limited support for CRT as a possible augmentation to SUD treatment and may not generalize to outpatient treatments. Nevertheless, the National Institute on Drug Abuse (NIDA) was sufficiently encouraged by these findings as well as the large neuroscience literature on the effects of SUD's on cognition to issue an RFA entitled "Cognitive Remediation Approaches to Improve Drug Abuse Treatment Outcomes (R21)". Our group (PI: [name]) was awarded an R21 pilot grant under this mechanism to demonstrate feasibility of CRT for outpatients with SUDs and to determine effect sizes on neurocognitive and substance abuse outcomes.

In this NIDA funded study, CRT was combined with Work Therapy (CRT+WT) and compared with WT alone (Cognitive Training and Work Therapy in the Initial Phase of Substance Abuse Treatment; PI: [name]). Eighty-seven

Veterans from substance abuse outpatient services were screened for eligibility within their first 30 days of sobriety; 48 were administered baseline assessments and randomized on a 1:1 ratio into CRT+WT (n= 24) or WT only (n = 24). They were on average 50.2 years of age, 49.4% Caucasian and most had felony convictions (80.5%). Twenty-eight had Alcohol Use Disorder (AUD) and 20 had other SUDs (amphetamine, cocaine, opiates). Our analysis of baseline neurocognitive assessments revealed high baseline rates of cognitive impairment, with 87.5% showing a clinically meaningful decline (1 SD) from a measure of their pre-morbid IQ on at least one cognitive measure. Moreover, 77.1% showed decline on 2 measures or more and the median was 3 measures out of 14 possible measures showing such a decline. Interestingly the highest rates of significant cognitive decline and impairment were on measures of verbal (50%) and non-verbal (45.8%) learning and memory with measures of executive function (41.7%) and working memory (37.5%) commonly

Figure 1. Work+Cog Working Memory increases over time.

Note Simple slopes analyses of rates of change found Working Memory slope for Work+Cog was statistically significant ( $y = .785, se=.314, p = .01$ ). Slope for Work Only was not statistically different from zero ( $y = -.335, se=.398, p = .264$ ). Difference between groups' baseline scores was not statistically significant ( $y = 3.445, se=2.627, p = .196$ ). TimeXCondition is statistically significant ( $F = 6.7, n < .01$ )

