**Procedures:**

Informed Consent and HIPAA authorization will be obtained according to procedures approved by the VACHS IRB. A certificate of confidentiality will be requested.

Randomization: Participants will be randomized into CRT+IDC or Game-Play Placebo+IDC conditions. Randomization will be stratified by neurocognitive deterioration (Yes/No) based on having 3 or more baseline cognitive measures greater than 1 SD below premorbid estimate (3 was the median number of measures below expected value in the pilot R21 study described above). Variable block randomization tables will be created based on computer generated blocks using random permuted blocks of 2 to 6 by our statistician from Yale Center for Analytic Science. Sealed envelopes containing the randomization by participant entry number will be created and opened when a participant's pre-randomization procedures are completed.

Assessments Procedures: Measures are listed in the table above. Preliminary screening will be performed with a brief interview usually by phone that describes the inclusion and exclusion criteria in simple language and asks if the individual believes he/she meets criteria. After informed consent, participants will undergo DSM-V diagnostic procedure with the M.I.N.I diagnostic interview adapted to DSM-V., the WTAR to determine reading level and pre-morbid IQ estimate and a thorough demographic and psychosocial interview to determine whether they are eligible for the study according to inclusion and exclusion criteria. Information from medical records and referring clinicians are also used. During the active intervention participants will have weekly Breathalyzer tests and a weekly TLFB Alcohol Use Calendar. Critical events will also be recorded along with on-going process data about participation in procedures and response to cognitive training. Treatment utilization will be tracked weekly and at follow-ups by chart review and interview. Baseline assessments will be repeated at 3 months and 6 months. A briefer battery of cognitive tests will be performed at 7 weeks. The participant time line is shown in the table below:

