Sample size: We plan to screen approximately 150 Veterans and recruit 110 Veterans (after telephone screen) with a current and primary DSM-V AUD who are within the first 30 days of recovery and expect that 90 will be eligible for randomization after baseline testing. We expect better than a 90% retention rate at the 3 month time point, and thus expect to have more than 80 individuals for the primary analysis. Assuming equal loss-to-follow-up in each of the two treatment arms, we will have at least 40 individuals per group. Using data

from our pilot study and the study done by Bowen et al., we estimate mean Days of Alcohol Use in the Placebo + IDC arm to be 4 and the number of Heavy Drinking Days to be 3 at 90 days. Using PASS 12 (Kaysville, Utah) Poisson regression procedure, and assuming an over-dispersion parameter of 2 for days of use and 4 for heavy drinking days, we will be able to detect a 37% reduction in days of use and a 55% reduction in days of heavy drinking with 80% power and a type I error rate of 5% for each outcome in the CRT+IDC arm compared to the Game-Play Placebo + IDC arm. Stratification on neurocognitive functioning was not factored into the sample size calculations. In most situations, stratification will increase precision, and thus we will have a conservative estimate of the detectable effects. Given that we expect to lose another 5-10% of individuals to follow-up, we will have less power to detect the same effect size at 6 month time point.

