Analysis Plan: We will use a Poisson regression model accounting for over-dispersion to compare the CRT+IDC arm to the Game-Play Placebo+IDC arm on the primary outcomes: Days of Use and Days of Heavy Drinking at 90 days (Ho1). We will use the same model to compare the CRT+IDC arm to the Game-Play Placebo+IDC for the 6 month time point, a secondary endpoint (Ho2). We will conduct sensitivity analysis using a negative binomial model and assess any differences in the results compared to the Poisson model with over-dispersion. To evaluate neurocognitive functioning (global index; index of working memory; index of executive function, etc..), we will use generalized estimating equations and/or linear mixed models (if the data appear normally distributed) to account for the correlation between time points (baseline, 3 months, 6 months) for a given individual. We will test for a significant treatment arm by time interaction to determine whether the combination of CRT+IDC is more effective than Game-Play Placebo+IDC in improving neurocognitive outcomes (Ho3, Ho4). We use contrast statements to explore the individual time point effects. In all models, we will adjust for neurocognitive functioning (the stratification variable). We will use the Benjamini-Hochberg procedure to control the false discovery rate for all secondary outcomes keeping the overall level of significance at 0.05. However, given the limited sample size in this study, we do not expect to reach statistical significance unless there are large effects, especially for the secondary outcomes, and thus plan to use these results as hypothesis generating for a larger confirmatory study.

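### The drinking models adjust for baseline cognition only through a Yes/No deterioration flag, labelled as functioning, and leave the continuous baseline index unused

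*Combined protocol and SAP*

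**What the plan says.** All references are to the combined protocol and SAP.

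- **Analysis Plan paragraph.** "In all models, we will adjust for neurocognitive functioning (the stratification variable". This covers the over-dispersed Poisson models for Ho1 and Ho2, the negative binomial sensitivity models, and the longitudinal models for the cognitive indices.
- **Sample size paragraph.** The same name is used: "Stratification on neurocognitive functioning was not factored into the sample size calculations".
- **Procedures, Randomization.** "Randomization will be stratified by neurocognitive deterioration (Yes/No) based on having 3 or more baseline cognitive measures greater than 1 SD below premorbid estimate". The cut-point comes from the pilot: "3 was the median number of measures below expected value in the pilot R21 study". The reference value comes from "the WTAR to determine reading level and pre-morbid IQ estimate".
- **Data Management paragraph.** The cognitive tests are combined into domain scores and one composite index. Arms are compared at baseline, and any variable that differs significantly becomes a covariate.
- **Purpose and Background.** Cognitive deficits on entry to treatment are said to reduce its benefit, and executive and prefrontal problems are linked to worse alcohol outcomes.

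**The concern.** The name and the variable do not match. The flag records whether a person has fallen below their own premorbid estimate on enough tests. Two people with identical scores can be in different strata if their reading-based estimates differ. In the same paragraph, *neurocognitive functioning* also names the continuous outcome indices, so one term covers two different things.

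The second issue concerns the primary analysis. The cognitive models carry the baseline score as a time point. The drinking models carry no prespecified baseline cognitive score, only the flag. Yet the plan's rationale is that cognitive impairment on entry affects alcohol outcomes, which makes the baseline index a natural prognostic covariate. Leaving it out gives up precision in a trial that the authors themselves describe as limited in size. A report following the plan's wording would also describe the drinking results as adjusted for cognitive functioning, when the adjustment was for a binary decline flag.

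**Working it through.** **1. Reproduce the plan's detectable effects.** Inputs from the Sample size paragraph: N = 80 (40 per arm), 80% power, 5% type I error (sidedness not stated; two-sided reproduces), control means μ₀ of 4 and 3 days, over-dispersion φ of 2 and 4. For 1:1 Poisson regression:

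N = φ·[1.96·√4 + 0.842·√(2 + 2/RR)]² / (μ₀·(ln RR)²)

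Solving at N = 80 gives reductions of 36.9% (stated 37%) and 54.2% (stated 55%). The plan's figures reproduce, and they use no covariate.

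**2. Power at the stated effects.**

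Power = Φ{[|ln RR| − 1.96·√(4φ/(μ₀N))] / √(φ(2 + 2/RR)/(μ₀N))}

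- Days of use, RR = 0.63: (0.462 − 1.96 × 0.158)/0.180 = 0.846, power 80.1%.
- Heavy drinking days, RR = 0.45: (0.799 − 1.96 × 0.258)/0.328 = 0.892, power 81.4%.

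**3. Add a baseline index that explains a share R² of residual outcome variance.** Replace φ by φ(1 − R²). R² is an assumption; the documents give no value.

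| R² | Days of use | Heavy drinking days |
|---|---|---|
| 0 | 80.1% | 81.4% |
| 5% | 81.9% | 83.0% |
| 10% | 83.8% | 84.7% |
| 20% | 87.5% | 88.1% |

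The comparison is with no covariate at all, so each gain is an upper limit for its R².

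**4. How much the flag may already capture.** Let r² be the squared correlation between flag and index. The documents report none, so it was simulated for 14 measures.

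- *Scores compared directly with the premorbid estimate:* 63 scenarios with 55% flagged and a median count of 3. Premorbid SD was 0.6-1.0, premorbid loading 0.3-0.7 and inter-measure correlation 0.3-0.5, with and without between-person variation in decline. r² ran from 0 to 36%, median 13%. The Background reports "87.5% showing a clinically meaningful decline (1 SD) from a measure of their pre-morbid IQ on at least one cognitive measure" and "77.1% showed decline on 2 measures or more and the median was 3 measures out of 14 possible measures"; in the ten scenarios nearest those pilot shares, r² was 0-19%.
- *Scores compared with a value predicted from the premorbid estimate:* inter-test and test-premorbid correlations of 0.3-0.5 gave r² of 23-52%.
- *Ceiling:* a median split of a single normal score keeps at most 2/π = 64% of its variance.

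**5. Gain beyond the flag.** If the flag predicts drinking only through the index, the variance of the arm effect is multiplied by (1 − R²)/(1 − R²·r²).

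- R² = 10%, r² = 0: 0.90, worth 80 × 0.10 = 8 participants. Power for days of use goes from 80.1% to 83.8%.
- R² = 10%, r² = 36%: 0.90/0.964 = 0.934, worth 80 × 0.066 = 5.3 participants. Power goes from 81.4% with the flag to 83.8%.
- R² = 10%, r² = 52%: 0.90/0.948 = 0.949, worth 80 × 0.051 = 4 participants. Power goes from 82.0% to 83.8%.
- R² = 5%, r² = 52%: 0.95/0.974 = 0.975, worth 80 × 0.025 = 2 participants. Power goes from 81.1% to 81.9%.

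**The case against.** The case for leaving the plan alone is substantial.

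- Adjusting for the stratification factor is right for this randomisation. The sentence identifies its covariate in parentheses and Procedures defines it, so an analyst would fit the correct variable. This stands: the label is a wording fault.
- Deterioration is a reasonable construct, because the rationale speaks of deficits and impairments. If decline rather than level predicts drinking, the formula in step 5 does not apply. This stands as a limit on the size.
- The prognostic strength is assumed. The pilot's cognitive gains came with no difference between arms in substance use outcomes. That does not rule out a baseline association, but it gives no ground for expecting a strong one.
- A significantly imbalanced baseline index would enter as a covariate. That is true, but the rule responds to chance imbalance rather than prognostic value, and the plan thinks such differences unlikely. It does not replace prespecification.

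A reader might infer more than the documents support:

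- *That the drinking models are not adjusted for baseline cognition.* The flag is built from the baseline tests, so the adjustment is coarse, not absent.
- *That the flag hardly tracks functioning, or mainly reflects reading ability.* Both depend on unstated correlations and on direct comparison of scores with the premorbid estimate. The plan's own gloss on the cut-point refers to an expected value, which fits a predicted-score reading at least as well. Under that reading r² is 23-52%, and a link with reading ability is not expected if decline is independent of the premorbid estimate.
- *That the treatment comparison is biased.* Omitting a prognostic covariate from a randomised comparison costs precision only.

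**Conclusion.** The point holds as one of labelling and efficiency. Two parts rest on the text alone: the Sample size and Analysis Plan paragraphs misname the stratification factor, and that factor is the only prespecified covariate in the drinking models although a continuous baseline composite is available. The size rests on assumption. With the index explaining 5-10% of outcome variance, power rises to at most about 82-84% for days of use (from 80.1%) and 83-85% for heavy drinking days (from 81.4%), with less to gain where the flag already carries the information. The benefit is modest and undocumented, but nearly free. Neither the validity of the trial nor its stated detectable effects is in question.

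**What to change.** In the Analysis Plan paragraph, replace the adjustment sentence with:

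> All models include the stratification factor, neurocognitive deterioration (Yes/No). The Poisson and negative binomial models for Ho1 and Ho2 also include the continuous baseline composite neurocognitive index.

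Use the name *neurocognitive deterioration* for the factor in the Sample size paragraph as well, and keep *neurocognitive functioning* for the outcome indices. The index then enters whether or not the arms differ on it at baseline.

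Cost: a wording change and one degree of freedom in about 80 participants. The tests are already given at baseline and the composite is already planned, so nothing new is collected. Randomisation and stratification are unchanged.
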